9.4 Statistical Analysis Plan

9.4.1 General

Descriptive statistics will primarily be generated to summarize the data. For continuous variables, e.g., immunological parameters, GD2 target antigen expression etc., descriptive statistics may include the number of subjects reflected in the calculation (n), mean, standard deviation, median, minimum, and maximum; frequencies and percentages may be displayed for categorical data (e.g., toxicities, phenotype of cellular infiltrate, etc.). All data analyses will be performed using SAS[®] (SAS Institute Inc., Cary, North Carolina) version 8.2 or greater and R version 1.91 or greater, a publicly available statistical analysis environment (<http://www.r-project.org>).

9.4.2 Baseline Comparability

All measurements (variables) collected at baseline will be summarized and compared between study arms. If the pre-treatment value is missing, the measurement recorded at the screening visit will be substituted. Significant unbalances found between study arms may be considered as covariates in exploratory analyses of primary endpoints (i.e., pathology evaluations of necrosis, apoptosis, and cellular infiltrate).

9.4.3 Demographics

All demographic variables (e.g., gender, age, weight, etc.) will be summarized by standard descriptive statistics, i.e., in terms of means, standard deviations, medians, and ranges for variables on a continuous scale, and in terms of frequency tables for variables on a categorical scale.

9.4.4 Primary Endpoints

Pathology evaluations of necrosis, apoptosis, and cellular infiltrate will be summarized in frequency tables (for each study arm). The proportions of subjects with tumor tissues classified as *positive* (i.e., the microscopic evaluation is classified as “low”, “medium”, or “high”) will be reported along with the corresponding 90% confidence intervals. The comparisons of pathology evaluations between the two study arms will be performed by Fisher’s exact test. For subjects in treatment group B, tumor tissues from biopsies obtained at study entry (pre-study biopsies) will be compared to surgically resected tumor tissues obtained after the first course of IC treatment. Paired comparisons of necrosis, apoptosis, and cellular infiltrate pathology evaluations will be performed using McNemar’s test.

Time to recurrence and overall survival will be summarized using point estimates of the median time to recurrence/overall survival and associated 90% confidence intervals. The data will be presented graphically using Kaplan-Meier plots. The two-year recurrence free survival rate and two-year survival rate will be reported along with the corresponding 90% confidence interval. Time to recurrence and overall survival will be contrasted to historical controls (47,49-53) as well as data from comparable subject groups being observed following surgically induced CR that may be published now and when the data from the present study are being analyzed.

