9.3.1 Randomization/Stratification

The randomization will be based on a permuted block of size 4, stratified by type of surgical resection (“extensive” vs. “non-extensive”). “Extensive” surgical resection is defined as: Resection requires thoracotomy, laparotomy or excision of deep soft tissue metastases in 3 or more anatomic locations. “Non-extensive” surgical resection is defined as: Resection requires cutaneous/subcutaneous excision and/or excision of deep soft tissue disease in only 1 or 2 locations.

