9.3.2 Sample Size/Accrual Rate

The first primary objective of this study is to evaluate the histological evidence of anti-tumor activity of hu14.18-IL2 by comparing pathological endpoints between the two groups after dichotomizing the evaluation of apoptosis, necrosis and cellular infiltrate into *positive* (i.e., the microscopic evaluation is classified as “low”, “medium”, or “high”) or *negative* (i.e., the evaluation is classified as “none”) using Fisher’s exact test. With eight subjects per group, a difference of 70% in the proportions of subjects classified as *positive* for necrosis, apoptosis, or cellular infiltrate between the two study arms will be detected with at least 82% power at a two-sided significance level of 0.1. A difference of 60% will be detected with at least 64%. Smaller differences are unlikely to be detected as statistically significant. The sample size chosen is sufficient to provide accuracy in the estimated rate of subjects classified as *positive*. Specifically, with eight subjects per group, the standard error of the proportions of subjects classified as *positive* necrosis, apoptosis, or cellular infiltrate for each group will be at most 0.18.

The second primary objective of this study is to evaluate the time to recurrence (duration of remission) and overall survival relative to historical control data described in Section 1.3.3. This study is not designed to detect differences in time to recurrence or overall survival between the two study arms. Instead, time to recurrence and overall survival time of both arms combined will be compared to historical controls qualitatively. Time to recurrence and overall survival time will be summarized using point estimates of the median time to recurrence/overall survival time and associated 90% confidence intervals. Furthermore, the two-year recurrence free survival rate and the two-year survival rate will be reported along with the corresponding 90% confidence intervals. The following table gives (two-sided) Wilson’s score 90% confidence intervals for the two-year survival/two-year recurrent-free survival rates, assuming a total sample size of 16 subjects.

Table 9: Ninety percent confidence bounds for two-year survival/two-year recurrent-free survival rates

Observed number of subjects alive/recurrent-free after 24 months	Proportions of subjects alive/recurrent-free after 24 months	Lower 90% confidence limit	Upper 90% confidence limit
2	0.12	0.04	0.32
4	0.25	0.12	0.45

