6	0.38	0.21	0.58
8	0.50	0.31	0.69
10	0.62	0.42	0.79
12	0.75	0.55	0.88
14	0.88	0.68	0.96

Therefore, with a sample size of 16 subjects, the 90% confidence interval for the two-year survival/two-year recurrent-free survival rate will be no wider than 38%.

Secondary endpoints of this pilot study include adverse events, immunological parameters, density & phenotype of cellular infiltrate and expression of GD2 target antigen, and IFN- γ expression. Assuming a total sample size of 16, the probability of observing at least one incidence of Grade ≥ 3 toxicity is 81%, if the true toxicity rate is 10%. Analogously, the probability of observing at least one incidence of Grade ≥ 3 toxicity is 93%, if the true toxicity rate is 15%. Immunological parameters will be measured on a continuous scale. Assuming a sample size of eight subjects per

study arm, a difference of 1.5 standard deviation units in magnitude will be detected with 80% power at a two-sided significance level of 0.05 (based on a two-sample t-test). A difference of only 1.25 standard deviation units will be detected with 63%. Smaller differences are unlikely to be detected as statistically significant.

In order to account for “unevaluable” subjects and drop-outs (e.g., patients without an evaluation following course 2 of IC treatment), we will accrue up to 20 eligible subjects (10 per arm) in total. Based on our past experience with advance melanoma subjects treated at UWCCC, we expect to accrue 20 eligible subjects within 24 months. The minimum follow-up period will be 12 months after the last subject has entered the study.

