The analysis of GD2 target antigen expression, density and phenotype of cellular infiltrate, vascularity, IC binding, and IFN- γ expression will be exploratory by necessity. Expression levels for these will be summarized in terms of means, medians, standard deviations and ranges where possible. Comparisons of expression levels between the two groups will be performed using two-sample t-tests (after appropriate transformations) and/or non-parametric Wilcoxon Rank Sum tests. Phenotypes of cellular infiltrate will be summarized in tabular format. Differences of phenotype frequencies between the two groups will be evaluated using Fisher's exact tests.

Augmentation of T cell reactivity to autologous tumor or to known melanoma antigens will be analyzed descriptively. The level of significance of each hypothesis test involving secondary endpoints will be 0.05. Due to the exploratory nature of these analyses, there will be no multiplicity adjustment.

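### With 8 evaluable subjects per arm, Fisher's exact test at two-sided 0.10 spends at most 2.8% type I error and falls slightly short of the stated minimum power; Boschloo's test would recover power, but needs a multiplicity rule alongside it.

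*Combined protocol and SAP*

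**What the plan says.** Section 9.3.2 reduces each pathology feature (necrosis, apoptosis, cellular infiltrate) to positive or negative and names Fisher's exact test. Section 9.4.4 repeats the choice: "The comparisons of pathology evaluations between the two study arms will be performed by Fisher’s exact test".

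The power statement in 9.3.2 begins "With eight subjects per group, a difference of 70% in the proportions" and says that this difference "will be detected with at least 82% power at a two-sided significance level of 0.1". It continues "A difference of 60% will be detected with at least 64" percent, then warns that smaller effects would probably be missed. No background positive rate is given, so the claim of at least that power has to hold at every rate.

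On numbers, sections 5.1 and 9.3.2 aim for eight evaluable subjects per arm, and 9.3.2 adds "we will accrue up to 20 eligible subjects (10 per arm) in total".

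On multiplicity, 9.4.5 says "Due to the exploratory nature of these analyses, there will be no multiplicity adjustment", but that sentence concerns secondary endpoints. Nothing is said about the three primary pathology features.

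**The concern.** Fisher's test conditions on the total number of positive tumors. With eight subjects per arm, each total allows only a few p-values, so a nominal 10% test can run far below 10%. This is the only primary comparison with a power calculation, in a pilot meant to show whether activity justifies further work. The sponsor chose a lenient 0.10 level. If most of it goes unspent, real effects are missed for no gain that the plan asks for, and part of the stated detection limit comes from the test and not from the sample size.

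**Working it through.** **Inputs.** 8 v 8, two-sided 0.10, differences d of 0.70 and 0.60 (9.3.2). The lower positive rate p is not given (9.3.2 states only "a difference of 70% in the proportions of subjects classified as" positive), so it is scanned over its whole range: 0 to 0.30 for d = 0.70 and 0 to 0.40 for d = 0.60.

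**Formulas.** Let R be the set of tables (x, y positives) that a test rejects, out of 9 × 9 = 81.
- Size at common rate p: Σ over R of C(8,x) C(8,y) p^(x+y) (1−p)^(16−x−y), maximised over p.
- Power at rates p and p+d: Σ over R of Bin(x; 8, p) × Bin(y; 8, p+d), minimised over p.

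**1. The plan's figures.** Exact Fisher power at p = 0.10 is 81.2% (70 points) and 65.7% (60 points). A continuity-corrected normal approximation with n′ = (n − 1/d)²/n gives minima of 82.1% and 62.5%:
- d = 0.7: n′ = (8 − 1.429)²/8 = 5.40
- d = 0.6: n′ = (8 − 1.667)²/8 = 5.01

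Both routes come within two points of the stated 82% and 64%, so those figures are roughly right for some rates. They are not minima of the exact test.

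**2. Fisher at 0.10.** It rejects 0 v 4 or more, 1 v 6 or more, 2 v 7 or more, 3 v 8 and 4 v 8, with mirror images. Counting arrangements by total number of positives:

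| Total | 4 | 5 | 6 | 7 | 8 | 9 | 10 | 11 | 12 |
|---|---|---|---|---|---|---|---|---|---|
| Rejected arrangements | 140 | 112 | 56 | 464 | 130 | 464 | 56 | 112 | 140 |

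For example, a total of 7 gives 2×8 (0 v 7) + 2×8×28 (1 v 6) = 464. The sum Σ count × p^T (1−p)^(16−T) peaks at p = 0.325 with value **0.0279**.

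Minimum power is **80.0%** for 70 points (at p = 0.15) and **61.4%** for 60 points (at p = 0.20). It is below 82% only for p of about 0.087 to 0.213, and below 64% only for p of about 0.120 to 0.280.

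**3. Boschloo at 0.10.** It orders tables by Fisher's p-value and takes the largest region whose size stays within 0.10. It keeps every Fisher rejection and adds 0 v 3 (112 arrangements), 1 v 5 (896), 2 v 6 (1,568), 3 v 7 (896) and 5 v 8 (112), mirror images included. The size peaks at p = 0.276 with value **0.0822**. Minimum power is **92.2%** and **80.1%**.

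**4. Other arm sizes.** Same formulas with the sizes changed, minimised also over which arm has the higher rate. Power is shown for 70 / 60 points.

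| Arms | Fisher: max size | Fisher: min power | Boschloo: max size | Boschloo: min power |
|---|---|---|---|---|
| 8 v 8 | 2.8% | 80.0 / 61.4 | 8.2% | 92.2 / 80.1 |
| 7 v 8 | 4.6% | 83.1 / 66.1 | 8.4% | 88.8 / 75.5 |
| 8 v 9 | 5.2% | 90.2 / 75.9 | 8.9% | 92.1 / 79.8 |
| 10 v 10 | 4.2% | 93.3 / 80.5 | 8.9% | 96.1 / 87.3 |

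**5. Three features at 8 v 8.** The bound on any false positive is 3 × 0.0279 = 8.4% with Fisher and 3 × 0.0822 = 24.7% with Boschloo. If the features were independent, the figures would be 1 − (1 − 0.0279)³ = 8.1% and 1 − (1 − 0.0822)³ = 22.7%. Boschloo at 0.10/3 = 0.033 per feature gives exactly Fisher's 8 v 8 rejection region, hence the same size and power.

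**The case against.** Fisher's test is a valid level-0.10 test, and the plan names it consistently. In a randomised trial, under the null that treatment changes no subject's result, the total number of positives is fixed, so conditioning on it is a defensible frame. This stands. A reader might infer that the plan uses a wrong test or is badly underpowered. The documents do not support that: the shortfall is at most 2.0 and 2.6 points, and only over a middle band of rates.

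8 v 8 is also unfavourable to Fisher. Evaluability under section 5.1 requires surgery and two courses, whereas the pathology comparison needs only resected tumor, and accrual may reach 20. The analysed sizes may therefore differ from 8 v 8. At 7 v 8, 8 v 9 and 10 v 10 Fisher meets the stated 82% and 64%. This stands too: the 12- and 19-point gains cannot be promised in general, and a flat claim of at least 80% for 60 points would fail at 8 v 9 even with Boschloo (79.8%).

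Last, Fisher's conservatism happens to hold the three-feature error down. A reader might infer that changing the test costs nothing. At 0.10 per feature it does cost something: a result such as 0/8 v 3/8 (Fisher p = 0.20, Boschloo p = 0.082) would become significant.

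The comparison also sits in a pilot whose analysis is mainly descriptive, with 90% confidence intervals for each arm reported regardless of the test. That lowers the urgency but does not make the stated power correct.

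**Conclusion.** The point holds as an efficiency and accuracy matter, not as a validity error. At the planned 8 v 8, Fisher uses at most 2.8% of a 10% budget, and its minimum power (80.0% and 61.4%) is slightly below both stated minima. Boschloo at the same level keeps the error at or below 8.2% per feature and raises the minima by 12.2 points (92.2 − 80.0) and 18.7 points (80.1 − 61.4).

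This rests on independent binary results, on the unstratified comparison as planned, on a minimum taken over all background rates because none is stated, and on exactly eight subjects per arm. At 8 v 9 the gain falls to 1.9 and 3.9 points. Whether the full gain is available depends on an unstated choice: 0.10 for each feature, or 0.10 across the three. Under the second reading with a 0.10/3 split, Boschloo and Fisher coincide at 8 v 8 and nothing is gained there.

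**What to change.** Before any between-arm pathology comparison is seen, amend 9.3.2 and 9.4.4 as follows.

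1. Name one test for the between-arm positive/negative comparison: Boschloo's unconditional exact test, two-sided 0.10 per feature, with its ordering by Fisher's p-value written down. Do not leave a choice of unconditional tests open, because they can differ when the arms are not 8 v 8.
2. Restate power as at least 92% (70 points) and at least 80% (60 points), labelled as minima over background rates for 8 v 8. Add that the gain over Fisher is smaller at some other sizes, for example 92.1% and 79.8% against 90.2% and 75.9% at 8 v 9.
3. State the rule for the three features. Either test each at 0.10 without adjustment and acknowledge up to about a 25% chance of any false positive, or test each at 0.10/3. The second option reproduces Fisher's size and power at 8 v 8, but not at other sizes: at 8 v 9 its minima are 76.7% and 56.5%.
4. If Fisher is kept, change the power statement to at least 80% and at least 61%, and note the attained size of at most 2.8% at 8 v 8.

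The cost is SAP wording and a short program. Section 9.4.1 names SAS and R but does not show that the stated versions include Boschloo's test; with 81 tables it can be coded directly. No extra subjects, drug or tissue are needed. The price of the unadjusted option is the higher three-feature error in item 3.

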9.4.5 Secondary Endpoints

The number and severity of toxicity incidents will be analyzed descriptively in tabular format. Immunological parameters, i.e., lymphocyte counts, NK/ADCC, soluble IL2, anti-idiotypic antibodies, and anti Fc-IL2, will be summarized by standard descriptive statistics in terms of means, standard deviations, medians and ranges for each measurement time point (see Section 7.3) and group separately. Within each group, differences between pre-IC treatment values and post-IC treatment values will be evaluated by paired t-tests and/or non-parametric Wilcoxon test.

Comparisons of immunological parameters between the two study arms will be performed by two-sample t-tests. Furthermore, longitudinal data analyses of immunological parameters will be performed to incorporate the time effect. Specifically, linear and/or nonlinear mixed effect models with subject specific random effects and generalized estimating equations (GEE) models with identity link and exchangeable (working) correlation structures will be used to account for the correlation between repeated measurements of immunological parameters. Missing data may be imputed using regression type imputation techniques. For immunological parameters not conforming to the assumptions of parametric analysis, the non-parametric Wilcoxon Rank Sum test will be used for comparing the two study arms. The association between the various immunological parameters will be examined by computing Spearman's rank correlation coefficients and linear or nonlinear regression techniques. Immunological parameters will be correlated with clinical endpoints by fitting Cox regression models (for clinical endpoints overall survival & time to recurrence) and logistic regression analysis models (for clinical endpoints toxicity and histological evidence of anti-tumor activity). The data of all immunological parameters will be presented graphically where possible (boxplots, histograms, profile plots and scatterplots).

The analysis of GD2 target antigen expression, density and phenotype of cellular infiltrate, vascularity, IC binding, and IFN- γ expression will be exploratory by necessity. Expression levels for these will be summarized in terms of means, medians, standard deviations and ranges where possible. Comparisons of expression levels between the two groups will be performed using two-sample t-tests (after appropriate transformations) and/or non-parametric Wilcoxon Rank Sum tests. Phenotypes of cellular infiltrate will be summarized in tabular format. Differences of phenotype frequencies between the two groups will be evaluated using Fisher's exact tests.

Augmentation of T cell reactivity to autologous tumor or to known melanoma antigens will be analyzed descriptively. The level of significance of each hypothesis test involving secondary endpoints will be 0.05. Due to the exploratory nature of these analyses, there will be no multiplicity adjustment.

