5.0 TREATMENT PLAN

5.1 Accrual scheme

As outlined in Section 9.0 (Statistical Considerations), a total of 16 subjects will be treated with complete surgical resection and a minimum of 2 courses of protocol treatment. This may mean that additional subjects will need to be entered to account for subjects enrolled into the study and unable to

receive the complete resection and/or entered into the study and unable to receive the first two courses of protocol treatment. Accrual will be stratified to ensure that 8 evaluable subjects are entered into each arm and have received both surgery and 2 courses of study therapy. Stratification will also attempt to enroll similar numbers of subjects requiring extensive surgery and non-extensive surgery (see Section 4.4.8) into each of the treatment groups. The detailed clinical and laboratory monitoring is outlined in protocol Section 7.0 (Study Parameters), Tables 5 and 7.

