7.3 Immunological monitoring (Table 7A)

These *in vitro* studies will be done to monitor various aspects of the immune response to hu14.18-IL2. The time points mentioned in this section assume that treatment with hu14.18-IL2 will begin on day 1 and end on day 3.

7.3.1 Detection of anti-hu14.18-IL2 antibodies (anti-idiotypic and anti-FcIL2) will be performed on subjects' serum obtained at baseline and approximately 10 minutes prior to initiation of treatment, and serum samples on Days 3, 4, 8, and 29/1. Blood will be drawn in a red top tube, and kept refrigerated until serum is separated and stored frozen at -20° C.

7.3.2 As part of a laboratory substudy, additional biopsies will be requested from consenting subjects assigned to Group A (surgical resection after Course 1 of protocol therapy) who have readily accessible cutaneous or subcutaneous lesions. A "pre-treatment" biopsy will be a control tissue sample. In addition, we will ask for a "post-treatment" biopsy after receiving therapy for Course 1 but before surgical resection; according to the Schema above, this would be at approximately days 3-5. This tissue sample would depict any early inflammatory changes to the tumor that may not be present several days later at the time of surgery.

Readily accessible biopsies (cutaneous or subcutaneous lesion) will be obtained using 1% lidocaine for local anesthesia. The pretreatment biopsy of a cutaneous lesion will be compared both to the post-treatment biopsy and to tumor that is resected following treatment Course 1. The biopsies will consist of approximately 0.3 cm skin or subcutaneous samples (using a 3 or 6 mm punch). In the event the tumor nodules are larger than accessible using a 6 mm punch biopsy, a surgical consult will be obtained for excision of the nodule(s) using local anesthesia. These tumor biopsies, as well as all resected melanoma, will be evaluated as described in the Pathology Guidelines in Section 7.4.

7.3.3 Other *in vitro* immunological monitoring, including soluble IL2 receptor α levels, will be performed on subjects as per the assessment times in Table 7. Again, blood will be drawn using a red top tube, **and kept** refrigerated until the serum is separated, then stored frozen at -20° C.

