7.3.4 NK and ADCC testing will be done on selected patients with freshly collected PBMC at baseline (as a control), on day 8 of Courses 2 and 3, and on day 29/1 of Courses 2 and 3. The time point at day 8 was shown to be the peak for lymphocytosis and NK/ADCC function in our completed Phase I studies.

7.3.5 Lymphocyte cryopreservation for genetic testing will be done with lymphocytes obtained on day 8 of Course 2 and Course 3 in 7.3.4. As these time points are associated with lymphocytosis, the 10 cc of heparinized blood collected for NK/ADCC testing on those days will provide adequate PBMC numbers for the NK/ADCC assays and for cryopreservation of extra cells. These cryopreserved cells will be used for pilot analyses of DNA markers that may be relevant to anti-tumor effects or anti-id responses [e.g., analyses of immunoglobulin allotype alleles (93) of Fc receptor phenotype (94) or MHC-KIR gene mismatching].

7.3.6 Pilot studies of *in vitro* proliferative and cytotoxic responses of T-cells will be performed on selected subjects with 50 ml samples of heparinized blood obtained at baseline prior to Course 1, once within one week of the end of Course 2 (i.e., one week prior to starting Course 3), and once in the range of days 22-29 of Course 3. The lymphocytes will be obtained using 50 ml of heparinized blood left at **room temperature** until lymphocytes are separated, cryopreserved and stored in liquid nitrogen or in a -140° C ultracold freezer. When possible (based on availability of autologous tumor lysate for functional studies, growth of autologous melanoma cells, and/or HLA-A2 phenotype), subjects' PBMC will be evaluated for cytotoxicity against their own autologous melanoma cells,

tested for reactivity to the melanoma associated gp100 antigen by intracytoplasmic induction of IFN γ , and tested for reactivity to allogeneic melanoma lines. These studies will determine whether the 2 or 3 courses of hu14.18-IL2 treatment have induced detectable increases in T cell reactivity to autologous melanoma or to melanoma-associated antigens.

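### The between-arm tests of immunological parameters have no stated baseline term, although baselines are collected; adjusting for a pre-surgery baseline is a cheap but conditional gain in power

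*Combined protocol and SAP*

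**What the plan says.** Section 9.4.5 lists the immunological parameters as lymphocyte counts, NK/ADCC, soluble IL2 (measured as soluble IL2 receptor in Section 7.3.3 and Table 7A), anti-idiotypic antibodies and anti Fc-IL2. For the arm comparison it says "Comparisons of immunological parameters between the two study arms will be performed by two-sample t-tests", with the Wilcoxon rank sum test where parametric assumptions fail. Pre-treatment values are named only for the within-group paired tests. The paragraph then adds mixed models with subject-specific random effects and GEE models for the repeated measurements. It does not say whether baseline is a covariate, a response or left out. No post-treatment time point is named for the t-test.

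Section 9.3.2 rests the power on the same test: "a difference of 1.5 standard deviation units in magnitude will be detected with 80% power at a two-sided significance level of 0.05", stated to be "based on a two-sample t-test". It continues: "A difference of only 1.25 standard deviation units will be detected with 63" percent.

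Baseline samples are already planned. Section 7.3.1 takes "serum obtained at baseline and approximately 10 minutes prior to initiation of treatment" for the antibodies. Table 7A schedules a baseline soluble IL2 receptor sample, and Table 5 a baseline blood count with differential. For the cellular assays, Section 7.3.4 says "NK and ADCC testing will be done on selected patients with freshly collected PBMC at baseline (as a control"). Section 9.4.2 allows baseline covariates only for unbalanced variables, in exploratory analyses of the primary endpoints.

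**The concern.** With 8 subjects per arm, stable differences between people can make up much of the spread in a blood marker. If part of that spread is visible before treatment, a comparison that leaves baseline out carries it as noise and also carries any chance imbalance between the arms. The standard error of the baseline difference between arms is sqrt(2/8) = 0.5 SD, so an imbalance larger than 0.5 SD is expected in about one trial in three for each parameter.

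Section 9.3.2 itself accepts that differences below 1.25 SD are unlikely to be detected. If baseline predicts follow-up well enough, that limit can be lowered without more subjects or more samples. What is at stake is sensitivity in a set of exploratory comparisons.

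**Working it through.** **Inputs from the documents.** Section 5.1: "Accrual will be stratified to ensure that 8 evaluable subjects are entered into each arm". Section 9.3.2 adds a reserve for losses: "we will accrue up to 20 eligible subjects (10 per arm) in total". So n = 8 per arm, two-sided alpha 0.05, and differences of 1.5 and 1.25 SD.

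**Assumed input.** The documents give no correlation r between baseline and follow-up. It is varied from 0 to 0.7. Data are taken as normal.

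**Step 1: reproduce the plan's power.** For the unadjusted t-test the noncentrality is d × sqrt(n/2) on 2n − 2 = 14 degrees of freedom.
- d = 1.5: 1.5 × sqrt(4) = 3.0, power 79.7% (plan: 80%).
- d = 1.25: 1.25 × sqrt(4) = 2.5, power 64.3% (plan: 63%).

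Both agree with the plan within 2 points. A normal approximation (85.1% and 70.5%) and a one-sided t-test (88.6% and 76.8%) do not.

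**Step 2: ANCOVA with one baseline covariate.** The variance of the adjusted difference is (1 − r²) × (2/n + D²/W). Here D is the chance baseline difference between arms and W the pooled within-arm sum of squares of baseline. Degrees of freedom are 2n − 3 = 13. Power is averaged over 40,000 simulated baseline sets.

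| r | 1.25 SD (t-test 64.3%) | 1.5 SD (t-test 79.7%) |
|---|---|---|
| 0 | 60.7% | 76.1% |
| 0.2 | 62.4% | 77.8% |
| 0.3 | 64.7% | 79.9% |
| 0.4 | 68.1% | 82.9% |
| 0.5 | 73.0% | 86.7% |
| 0.6 | 79.3% | 91.4% |
| 0.7 | 87.4% | 96.0% |

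Break-even is near r = 0.3. At r = 0 the loss is 64.3 − 60.7 = 3.6 points and 79.7 − 76.1 = 3.6 points. The difference detectable with 80% power is 1.51 SD for the t-test. For ANCOVA it is 1.57 SD (r = 0), 1.50 (r = 0.3), 1.36 (r = 0.5) and 1.12 (r = 0.7).

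**Step 3: fewer subjects assayed.** NK/ADCC is tested in selected patients and the number is not given, so 5 and 4 per arm are assumptions. At 1.5 SD:

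| n per arm | t-test | ANCOVA r = 0 | r = 0.4 | r = 0.5 |
|---|---|---|---|---|
| 5 | 55% | 49% | 55% | 60% |
| 4 | 43% | 36% | 41% | 45% |

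Break-even moves to about 0.4 to 0.5. The loss at r = 0 is about 6 to 7 points here and about 5 points at 1.25 SD.

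**Step 4: change score as the alternative.** A t-test on change has noncentrality d × sqrt(n/2) / sqrt(2(1 − r)). At 1.5 SD with 8 per arm this gives 65.5% (r = 0.3), 79.7% (r = 0.5) and 94.9% (r = 0.7). Each is below ANCOVA at the same r, and below r = 0.5 it is worse than the plain t-test.

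**Step 5: which baseline.** Table 5, footnote 2, requires laboratory tests within 2 weeks before randomization, so the lymphocyte baseline precedes both surgery and drug. Table 7A, footnote 1, lets baseline fall anywhere from 3 weeks before randomization to just before study treatment. In the surgery-first arm (Group B in the Schema, labelled Group A in Section 9.3) that window includes time after the operation. Such a value could reflect the surgery, which the other arm has not yet had, and should not serve as the covariate.

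**The case against.** The strongest reply is that the t-test is not the whole plan. The mixed and GEE models cover the same parameters over time, and baseline is one of the scheduled measurements. A reader might infer from the t-test sentence that the plan decides to ignore baseline. The documents do not support that: the sentence does not say whether raw values or changes are compared, and the longitudinal models could carry baseline. What remains is that no between-arm analysis states how baseline is used.

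A reader might also infer that adjustment is free. It is not, as Steps 2 and 3 show. Both arms receive the same drug, and Section 1.3.5 reports lymphocytosis and a marked rise in soluble IL2 receptor under treatment. Whether baseline predicts those drug-driven values is unknown.

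The reach is limited too. Antibodies may be essentially absent at baseline, NK/ADCC may have fewer than 8 per arm, and T-cell reactivity is only to be described. Objective 2.2.2, on immune activation by the drug, is a before-and-after question that the paired tests already address. The explicit arm comparison in Objective 2.2.4 concerns tumor tissue. All of this stands and limits the weight of the point, but it gives no reason to leave the role of baseline open for the parameters that have a usable one.

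**Conclusion.** The point holds as a modest efficiency improvement. The unadjusted t-test is unbiased under randomization, its stated power is correct, and Section 9.4.5 calls these analyses exploratory and applies no multiplicity adjustment. Nothing in the documents supports calling the planned test an error.

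At 8 per arm the gain is about 9 points at 1.25 SD and 7 points at 1.5 SD if r = 0.5, and about 23 and 16 points if r = 0.7. These figures rest on normal data, a linear relation with baseline and an assumed r. The case is clearest for lymphocyte counts and soluble IL2 receptor. For NK/ADCC it depends on how many subjects are assayed.

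**What to change.** In Section 9.4.5:
- Name the post-treatment time point for the arm comparison.
- For lymphocyte counts and soluble IL2 receptor, replace the two-sample t-test with ANCOVA on arm and the subject's own baseline value, on the log scale if skewed.
- Do the same for NK/ADCC only if close to 8 per arm are tested; otherwise keep the unadjusted test.
- State that the same baseline enters the mixed and GEE models.
- Keep the unadjusted test for antibodies that are essentially absent at baseline, and leave T-cell reactivity descriptive.

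In Table 7A, footnote 1, restrict the baseline window in the surgery-first arm to before surgery. Table 5 needs no change.

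The cost is a short amendment to the analysis text plus a tighter sampling window, so it is more than one line in the SAP. No added subjects or samples are needed. The statistical price is one degree of freedom and the possible loss of power shown above if baseline proves uninformative.
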